### 5.3.5 Causal Relationship to Study Treatment

The investigator at each study site shall determine whether an event is causally related to the study treatment based on the following criteria and describe the basis for such a determination in the space for comments.

- (1) Not causally related: in cases where no temporal relationship exists between the occurrence of an adverse event and the study treatment or where the occurrence of the event can be explained by a medically appropriate reason other than the study treatment
- (2) Causally related: in cases where the above does not apply

## 5.4 Adverse Events Reporting

In the present trial, upon occurrence of a serious adverse event during the study treatment period, the treatment approach for the participant concerned shall be reviewed, and, if obtaining the study drug

information is deemed necessary, communications shall be appropriately carried out according to the procedure established at each study site.

#### 5.4.1 Serious Adverse Events Reporting

- (1) Upon occurrence of a serious adverse event, the investigator shall promptly notify the director, the institutional review board, and the secretariat of the hospital facility according to the Kyoto University Graduate School of Medicine and Faculty of Medicine and Kyoto University Hospital Medical Ethics Committee Operating Procedure 11 (Reporting of Serious Adverse Events/Safety Information in Medical Research Involving Human Subjects) (Appendix).
- (2) Complete a "Serious Adverse Event Reporting Form" on the data center's electronic data capture (EDC) system within 72 hours.
- (3) The secretariat, upon receiving a notification that a serious adverse event has occurred, shall notify the independent data monitoring board.
- (4) In cases where the serious adverse event is unexpected and associated with invasive medical intervention/research, the principal investigator shall publicly disclose information on the course of the event under the name of the hospital director and report to the Ministry of Health, Labour and Welfare periodically as the information becomes available using the form specified in the notification by the Research and Development Division of the Health Policy Bureau according to the Institutional Review Board Operating Procedure 11 for Kyoto University Graduate School of Medicine and Faculty of Medicine/Kyoto University Hospital (Reporting of Serious Adverse Events/Safety Information in Medical Research in Humans) (Appendix).
- (5) The principal investigator shall report, as appropriate, occurrences of any adverse drug reactions, infections, or problems due to the use of a pharmaceutical or medical device that has been approved for marketing in accordance with the "Pharmaceuticals and Medical Devices Safety Information Reporting System" provided in Paragraph 2 of Article 77-4-2 of the Pharmaceutical Affairs Law.

#### 5.4.2 Emergency Reporting

- (1) In the present trial, serious adverse events that meet the following description are subject to the emergency reporting requirement: any event occurring in the study treatment period that is life-threatening, requires emergency intervention, and for which information on whether the administration of betamethasone should be allowed is deemed necessary to review the treatment approach for the participant concerned.
- (2) Upon occurrence of an adverse event that is deemed "life-threatening and requiring emergency intervention as well as information on whether the administration of betamethasone should be allowed in order to review the treatment approach," the attending physician shall promptly notify the investigator. In the event the investigator cannot be contacted, the physician shall assume the responsibility of the investigator.
- (3) If an event is deemed "life-threatening and requiring emergency intervention as well as

information on whether the administration of betamethasone should be allowed in order to review the treatment approach,” the investigator shall report the event immediately to the director of the hospital facility.

- (4) The investigator shall follow the procedures provided in 4.8 for emergency code breaking and reporting.
- (5) The investigator (attending physician) shall record what transpired that led to the disclosure of the study drug allocation number and the disclosed information following Procedure 1 of 4.8 (emergency code breaking) or Procedure 2 (contacting the secretariat) on the Emergency Allocation Number Code Breaking Request Reporting Form, send it by email attachment or facsimile transmittal to the secretariat within 72 hours from the day of such a request, and retain the allocation number. The investigator shall also retain the sent file.

#### 5.4.3 Routine Reporting

Adverse events subject to the routine reporting requirement are shown in “5.1 Definition of Adverse Event.” If an adverse event subject to the routine reporting requirement occurs, the investigator (attending physician) shall record the required information on the CRF corresponding to the time period during which the event occurred and the Adverse Event Reporting Form and enter the information on the data center’s EDC by the deadlines for submitting each survey form.

In addition, wherever possible, the investigator (attending physician) shall follow up and document the outcome of the adverse event during the trial period on the survey form.

#### 5.5 Expected Adverse Events

See the package insert of Betamethasone Tablets (Appendix).

- 5.5.1 Adverse events that have been reported in association with the terminal-stage use of corticosteroids, particularly during long-term use, include oral candidiasis, subcutaneous hemorrhage, moon face, mood elevation, hyperglycemia, and gastrointestinal hemorrhage. Nevertheless, a wide variety of drugs are used in the terminal stage, making it unclear whether the adverse events are attributable to corticosteroids or other drugs such as nonsteroidal anti-inflammatory drugs (NSAIDs).
- 5.5.2 In a previous study of Decadron®, a 2-week randomized controlled trial with placebo, no significant difference in frequency of adverse events was reported between the active-drug group and the placebo group (41/62 vs. 44/58; P = .14).

## 6 Endpoints

### 6.1 Primary Endpoints

Fatigue (FA) score of EORTC QLQ-C15-PAL

The primary endpoint selected is the fatigue (FA) score, which represents a participant's QOL, on the EORTC QLQ-C15-PAL used to evaluate QOL on Day 7 after study commencement.

[Rationale for the choice of primary endpoint]

In the present trial, the subscale fatigue (FA) score as part of the assessment of patient QOL is considered the representative parameter of QOL and selected as the primary endpoint.

Palliative medicine is an approach aimed at improving QOL in patients and their families facing the issues related to a life-threatening disease. PS2/3 terminal-stage patients with advanced cancer-related fatigue who participate in the present trial share the treatment goal of QOL improvement. Thus, the QOL in participants will be assessed, with the score serving as an endpoint for assessing the efficacy of palliative medicine. The QOL questionnaire, however, is based on a multi-dimensional scale. The subscale fatigue (FA) has the greatest effect on QOL and is considered a representative parameter.

To reduce the load from EORTC on the patients receiving palliative care, the number of questions has been reduced from 30 in the EORTC QLQ-C30 used routinely to assess QOL in cancer patients to 15 in the disease-specific EORTC QLQ-C15-PAL for palliative care patients used to assess QOL in the present trial. Its Japanese version has been validated, with the validation results published. Registration with EORTC will take place before use.

### 6.2 Secondary Endpoints

#### 6.2.1 Efficacy Endpoints

(1) QOL-related scores other than the FA score on EORTC QLQ-C15-PAL

The efficacy of the steroid is confirmed if the EORTC QLQ-C15-PAL subscales of physical functioning, emotional functioning, appetite loss, and overall QOL showed improvements on Day 7 after study commencement.

(2) NRS (numeric rating scale)

The efficacy is confirmed if the fatigue NRS on Day 7 after study commencement showed an improvement.

(3) Survival time

Assess time to death with the day of enrollment (randomization) as the starting point. The efficacy is confirmed if the survival time is extended.

[Rationales for the choices of secondary endpoints (efficacy endpoints)]

(1) To assess improvements in the EORTC QLQ-C15-PAL subscales of physical functioning, emotional functioning, appetite loss, and overall QOL that are related to fatigue, in addition to the

fatigue subscale.

(2) To use the fatigue NRS, which is used by NCCN for screening fatigue, as one of the efficacy endpoints in the present trial.

(3) To ascertain in this 1-week study if the corticosteroid has efficacy in extending survival time.

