(2) The placebo-controlled design was chosen for the following reasons. 1) The study intends to provide patients appropriate palliative care regardless of whether intervention with a steroid is given and to determine the efficacy of the steroid's effect. Thus, to accurately assess the steroid's effect, placebo is needed as a comparator. The appropriate palliative care mentioned above refers to alleviation (or spiritual care in some facilities) of various distressing physical symptoms (e.g., treatment for dyspnea, in the case of lung cancer, or for nausea, vomiting, and constipation/diarrhea, in the case of gastrointestinal cancer) related to certain types of incipient cancer; pain, insomnia, and other physical symptoms associated with many end-stage cancers; and psychological and social issues. 2) Given that a placebo has the potential to provide a certain effect (placebo effect) in terms of alleviating fatigue, a subjective symptom, it is necessary to assess whether treatment with a steroid in the intervention group provides an added effect over and above the placebo effect. 3) We had the following discussion with collaborating physicians involved in palliative care about whether it is ethical to use a placebo control fatigue in PS2/3 terminal-stage patients with advanced cancer-related fatigue. Based on empirical knowledge derived from clinical practice, unlike pain therapy and other treatments that must be rendered promptly, no standard therapeutic intervention has yet been established to improve the quality of life (QOL) of fatigued patients, and the time to commence such a therapy may vary by about a week in normal clinical practice. Unlike therapies to treat pain, nausea, and dyspnea, which must be rendered promptly based on a specified procedure to determine when to commence treatment in clinical practice, a delay of about a week in giving the placebo group treatment with a steroid for fatigue in the present trial is not considered a material deviation from current clinical practice.

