#### 4.11 Concomitant Therapies

##### 4.11.1 Administration and Documentation of Concomitant Therapies

- (1) During the study period, follow the provisions provided below under “Prohibited Concomitant Therapies.”
- (2) Treat adverse events appropriately, at the discretion of the investigator (attending physician) at the study site where the event occurred.
- (3) Survey and document any concomitant therapies administered between eligibility verification and study treatment completion or discontinuation.

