##### 4.11.2 Prohibited Concomitant Therapies

During the study period, the administration for the first time of any of the medications or therapies described below is prohibited. In cases where a prohibited concomitant therapy cannot be discontinued

or must continue, withdraw the participant concerned from the study.

- (1) Oral or injectable adrenocortical hormone preparations other than the therapeutic agent used in the study
- (2) Oral administration of a synthetic corpus luteum hormone preparation
- (3) Surgery
- (4) Radiation therapy (except radiation therapy to alleviate symptoms)
- (5) Chemotherapy

[Rationales]

- (1), (2) Such hormone preparations can affect efficacy evaluations
- (3) Postoperative healing of surgical wounds is affected
- (4), (5) Decreased white blood cell count affects susceptibility to infections

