#### 4.13 Completion of Study

##### 4.13.1 Study Completion and Assessments

The investigator (attending physician), after performing the study treatment in a patient for one week

starting from the day of commencement, shall conclude the study treatment and complete the study in the participant.

On the day of study completion (Day 7), perform the observations, tests, and assessments required at study completion.

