#### 4.17.4 Information to be Reported at Completion of Study Treatment (Day 7)

- (1) With regard to the administration of concomitant treatments, the investigator (attending physician) is to record any drugs prescribed other than the study drug.
- (2) The investigator (attending physician) shall perform the ECOG PS assessment.
- (3) Ask participants to assess QOL by filling out the Japanese version of the EORTC QLQ-C15-PAL. Upon collecting a QOL questionnaire that has been filled out by a participant, check for any missing information immediately.
- (4) Ask participants to rate the severity of their fatigue on a scale from 0 to 10 on the NRS form for assessing the level of fatigue.
- (5) Perform a blood test, in principle, on Day 7 (acceptable range Days 8 to 14). However, depending on the patient's condition, it is acceptable to report data from a test conducted within one week from Day 7 on a day that is nearest to Day 7. The reported data are to include the date of the blood test, CRP, white blood cell count, hemoglobin, platelet count, and blood glucose.
- (6) For occurrence of adverse events, see “5. Adverse Events Assessment and Reporting.”
- (7) Participants shall record study drug compliance in the drug compliance diary (Appendix) and

submit the diary to the investigator (attending physician) on Day 7. The investigator (attending physician) shall check the drug compliance diary and transcribe the information into the CRF.

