#### 6.3 Exploratory Endpoints

Blood test (CRP, white blood cell count, hemoglobin, platelet count, blood glucose)

To investigate changes in the results of the blood tests (CRP, white blood cell count, hemoglobin, platelet count, blood glucose) between the most recent data on or before Day 0 and the most recent data on or after Day 7.

[Rationale for the choice of exploratory endpoint]

Several potential causes including anemia, psychologic problems, and cytokines have been proposed for the fatigue in terminal-stage cancer patients, but the causes are yet to be elucidated. Comparing CRP, white blood cell count, hemoglobin, platelet count, and blood glucose between the intervention group and the placebo group may provide data that indicate what the causes of fatigue might be.

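### Survival is read as confirming steroid efficacy, although steroid use after Day 7 is neither controlled nor recorded in either arm

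*Protocol*

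**What the plan says.** Section 6.2.1(3) measures survival from randomization to death and adds: "The efficacy is confirmed if the survival time is extended". The rationale beneath it attributes any gain to the corticosteroid.

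The rationale for placebo in 4.1 treats "a delay of about a week in giving the placebo group treatment with a steroid for fatigue in the present trial" as acceptable against current practice. Section 4.13.1 has the investigator give one week of treatment, after which the investigator "shall conclude the study treatment and complete the study in the participant". Section 4.11.2 prohibits starting "Oral or injectable adrenocortical hormone preparations other than the therapeutic agent used in the study" during the study period.

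On data collection, 4.11.1 instructs sites to "Survey and document any concomitant therapies administered between eligibility verification and study treatment completion or discontinuation". The schedule in 4.15 has no concomitant-therapy entry after Day 7. The outcome survey in 4.17.5 has three items: date of death or final outcome, outcome, and cause of death. Section 4.2 expects that survey to run for at least three to seven weeks after treatment and closes follow-up 16 weeks after the last enrolment.

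For the exploratory blood tests, 4.17.4(5) sets Day 7 in principle, accepts Days 8 to 14, and asks for the test nearest to Day 7 with its date. Note b in 4.15 caps the window at one week. Section 6.3 describes the follow-up value as "the most recent data on or after Day 7".

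**The concern.** The two arms are kept apart for one week, while survival is followed for weeks to months. The ethical case for placebo rests on steroid being available after a short delay, so later steroid use in the placebo arm is foreseeable. The protocol does not say whether patients in the steroid arm go on with it. What survival then compares is assignment to one blinded week of steroid against one week of placebo, each followed by whatever the patient happened to receive. That is a legitimate randomized comparison, but it is not the question that the wording and rationale of 6.2.1(3) claim to answer.

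The practical damage is greatest if survival does not differ. That result could mean that steroid has no effect on survival, or that most placebo patients started it in week 2. Without start dates the two cannot be told apart, and no statistical analysis plan can recover dates that were never collected. A lesser form of the problem touches blood samples from Days 8 to 14: study drug has then stopped and non-study steroid may have begun.

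**Working it through.** **1. The plan's own figure.** Section 4.2 gives 84 per group for 0.5 SD, two-sided 5%, power at least 90%. The normal formula gives n = 2(1.960 + 1.282)²/0.5² ≈ 84.1, or 85 when rounded up. Power at 84 per group is 0.900, and 168/0.8 = 210. The figure reproduces within rounding. It concerns the Day 7 fatigue score, which precedes any post-study steroid, so this point does not affect it. The protocol states no event count, hazard ratio or power for survival.

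**2. How long the contrast is protected.** Section 3.1 takes end stage as the last 1 to 2 months before expected death. I assume exponential survival with a median of 4 to 8 weeks. The share of deaths in week 1 is w = 1 − exp(−ln 2 × 1/median):

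- median 4 weeks: w = 0.159
- median 6 weeks: w = 0.109
- median 8 weeks: w = 0.083

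So only 8% to 16% of deaths fall in the one week in which the protocol keeps the arms apart.

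**3. Effect of later steroid use on the survival comparison.** Assumptions:

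- The true hazard ratio (HR) for steroid versus none is 0.70.
- The steroid arm continues steroid.
- A share c of placebo patients starts steroid after Day 7.
- All 210 enrolled patients die, which is the maximum possible.

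The average log HR is approximated as ln(0.70) × [w + (1 − w)(1 − c)]. Power is Φ(|ln HR| × √210/2 − 1.96), with √210/2 = 7.246. It counts only results favouring steroid, so its floor is 2.5%.

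For a median of 6 weeks and c = 0.5: ln HR = −0.3567 × (0.109 + 0.891 × 0.5) = −0.198, HR = 0.82, power = Φ(1.433 − 1.96) = 0.30.

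| c | Average HR (median 4 / 6 / 8 weeks) | Power |
|---|---|---|
| 0 | 0.70 / 0.70 / 0.70 | 73% |
| 0.25 | 0.76 / 0.76 / 0.76 | 53% / 52% / 51% |
| 0.5 | 0.81 / 0.82 / 0.82 | 32% / 30% / 29% |
| 1 | 0.95 / 0.96 / 0.97 | 6% / 5% / 4% |

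With a true HR of 0.80, power is 37% at c = 0, 14% to 15% at c = 0.5 and 3% to 4% at c = 1. Since c is not recorded, the trial cannot say where in this range it lies.

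**4. Blood tests.** Assume a 0.5 SD contrast, 84 per group, and every sample drawn in Days 8 to 14. If half the placebo arm already had full steroid exposure, the contrast is 0.25 SD and power is Φ(0.25 × √(84/2) − 1.96) = Φ(−0.34) = 0.37, against 0.90 at the full 0.5 SD. If all had it, the contrast is 0. This is an upper bound on the loss, because Day 7 is the default day and only some samples will be late.

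**The case against.** The strongest case on the other side has five parts.

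**Later steroid is not a planned step.** A reader might infer from 4.1 that placebo patients are scheduled to receive steroid after Day 7. The text does not support that: it argues that a week's delay is tolerable, and no section offers or requires steroid afterwards. This stands, and the point rests only on later use being possible and uncontrolled. If the prohibition in 4.11.2 were instead read as lasting until the whole study closes (15.1), it would sit badly with the delay argument in 4.1 and those sections would need reconciling. Later use would be unrecorded on either reading.

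**The survival rule runs one way.** Crossover mainly pulls the result toward no difference, so longer survival in the steroid arm would be a conservative finding. This largely stands, provided the steroid arm uses steroid after Day 7 at least as often as the placebo arm, which is also unrecorded. A reader might infer that the survival endpoint cannot confirm anything. The documents do not show that: the very low power appears only when the arms converge almost completely after Day 7, and with no crossover it is 73% at a true HR of 0.70.

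**Some of this may be captured.** Section 4.17.4(1) records other drugs prescribed at completion, which could include a steroid ordered at the Day 7 visit, and the forms themselves are appendices not shown. That helps at the margin, but 4.17.5 lists the outcome items and later steroid use is not among them.

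**The blood window is deliberate.** Section 4.17.1(13) rules out drawing blood solely for the trial, Day 7 is the default, and the test date is reported. The paired wording in 6.3 most naturally means closest in time, which agrees with 4.17.4(5). All of this stands. A reader might infer that the blood comparison could be reversed; nothing calculated here supports more than attenuation to zero.

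**Restricting the blood comparison would be worse.** Limiting the main comparison to samples taken before non-study steroid would select on a post-randomization event that may differ by arm. This stands, and the fix avoids it.

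**Conclusion.** The concern holds for survival. The comparison by assigned group is valid, but it does not estimate steroid versus no steroid, and the sentence in 6.2.1(3) and its rationale claim more than the design delivers. A null result is uninterpretable without knowledge of later steroid use. In the illustration, power at a true HR of 0.70 runs from about 73% to about 30% to about 5% as crossover goes from none to half to all. Those figures rest on assumed values for the hazard ratio, median survival, deaths and continuation in the steroid arm. The gap in data collection does not depend on any of them.

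The blood-test part is minor: a wording difference between 6.3 and 4.17.4(5), and off-treatment samples that can be separated by date. Only secondary and exploratory endpoints are involved. The change should be made because it is cheap and the missing dates cannot be supplied by analysis.

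**What to change.** 1. In 6.2.1(3), replace the sentence on confirmed efficacy and its rationale with a statement that survival from randomization is compared by assigned group as a supportive analysis, that steroid use after Day 7 is not controlled, and that the result is not an estimate of steroid versus no steroid.
2. Add to the outcome form in 4.17.5, for both arms: corticosteroid after Day 7 (yes/no) and start date.
3. In 6.3, use the wording of 4.17.4(5): the sample nearest to Day 7 within the permitted window. Keep every randomized patient with a sample in the main comparison. Add a sensitivity analysis by sample date (Day 7 versus Days 8 to 14), flagging samples taken after non-study steroid.

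The cost is two fields on an existing form, one sensitivity analysis and some rewording. No treatment rule, sample size or primary analysis changes.
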